1.1 PROTOCOL SUMMARY AND/OR SCHEMA

The purpose of this study is to define if the use of nightly sildenafil after radical prostatectomy results in better erectile function outcomes than nightly placebo for men who have undergone this operation. The study is also designed to compare erectile function outcomes between men using regular sildenafil and those using regular penile injections. Patients undergoing either laparoscopic or open nerve-sparing radical prostatectomy, who meet the inclusion and exclusion criteria, will be asked to participate in the study. Patients will be randomized into one of the three arms:

- 1. PRN Sildenafil Arm: Patients will use sildenafil 100 mg PRN for sexual relations. Patients will take placebo (blinded) at night regularly, except on nights when the sildenafil 100 mg pill is taken. There will be 40 patients in this group.
- 2. Nightly Sildenafil Arm: Patients will use sildenafil 100 mg PRN for sexual relations. Patients will take sildenafil 50 mg (blinded) at night regularly, except on nights when the sildenafil 100 mg pill is taken. There will be 80 patients in this group.
- 3. Combination Therapy Arm: Intracavernous injections of a trimix combination (Papaverine 30 mg/mL, Phentholamine 1 mg/mL, Prostaglandin E1 10 mcg/mL) will be injected three times a week and sildenafil 50 mg taken on the other four (non-injection) nights. Injection therapy can be used for the purposes of sexual relations. There will be 80 patients in this group.

Patients have the option of consenting either preoperatively or up to 6 weeks postoperatively.

Preoperative consent: Patients will be evaluated in the clinic and will complete the questionnaires at baseline (before surgery) and 3, 6, 9, 12, 18, and 24 months postoperatively. At 12 months postoperatively, all patients will stop treatment.

[figure not shown]

(RB PB

IRB#: 09-005 A(10)

Postoperative consent: Patients will be evaluated in the clinic and will complete the questionnaires retrospectively (after surgery) and 3, 6, 9, 12, 18, and 24 months after starting rehab. At 12 months after starting rehab, all patients will stop treatment.

The estimated time to completion of enrollment is 18-24 months. Patients will be monitored for a total of 24 months. Visits 3, 6, 9, 12, 18, and 24 months will have ± 2 week window.

	Baseline	3 Months (±2 weeks)	6 Months (±2 weeks)	9 Months (±2 weeks)	12 Months (±2 weeks)	18 Months (±2 weeks)	24 Months (±2 weeks)
Routine Blood Test	X						

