2.1 OBJECTIVES AND SCIENTIFIC AIMS

The objective of this study is to analyze the ability of 3 different pharmacological strategies to preserve the ability of men to achieve spontaneous (non-medication assisted) functioning erections after bilateral nerve-sparing radical prostatectomy.

Primary End-Point: Difference in the erectile function (EF) domain score of the International Index of Erectile Function (IIEF) between the 3 groups at 24 months.

Secondary End-Points:

- The time to return of spontaneous functional erections
- The time for patients to respond to oral erectogenic therapy
- The proportion of patients who have normalization of their erectile function (normalization of the EF domain of the IIEF)

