4.1 OVERVIEW OF STUDY DESIGN/INTERVENTION

4.2 Design

Patients undergoing either laparoscopic or open nerve-sparing radical prostatectomy, who meet the inclusion and exclusion criteria described in section 6.0, will be asked to participate in the study. Patients will be randomized into one of three arms and assigned a study number from CRDB (unrelated to their medical record number):

- life according to their ability; patients interested in using medication for sexual activity, will be offered sildenafil 100 mg to be used before intercourse on an asrequired basis. They will be given six 100 mg doses, per month, for a 12 month duration. Each patient in this group will use a placebo pill (blinded) each night, except on a night that 100 mg is taken for the purpose of sexual relations. This group can be considered to constitute "usual care" as it represents the current approach to penile rehabilitation in the community. We estimate, in the first 3 months, most people will not use sildenafil at all, after this, probably no more than once per week on average. The total expected dose in the PRN group is about 4000 mg over the course of the year. There will be 40 patients in this group.
- 2. Nightly Sildenafil Arm: Patients will be instructed to take sildenafil 50 mg (blinded) at night regularly, even when intercourse is not planned. These patients will be instructed to take 100 mg pill on occasions that they are interested in sexual relations. On these occasions, they will forego the usual nightly pill. They will be given six 100 mg doses, per month, for a 12-month duration. There will be 80 patients in this group.
- **3.** Combination Therapy Arm: Intracavernous injections of a trimix combination (Papaverine 30 mg/mL, Phentholamine 1 mg/mL, Prostaglandin E1 10 mcg/mL) will be injected three times a week, and sildenafil 50 mg taken on the other four

IRB PB

IRB#: 09-005 A(10)

(non-injection) nights. Injection therapy can be used for the purpose of sexual relations. There will be 80 patients in this group.

Preoperative consent: Patients will be evaluated in the clinic and will complete the questionnaires at baseline (before surgery) and 3, 6, 9, 12, 18 and 24 months after surgery. At 12 months postoperatively, all patients will stop treatment. Visits 3, 6, 9, 12, 18, and 24 months will have ± 2 week window.

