4.3 Blinding

Preoperative consent: Patients are to be consented and registered as pending prior to their surgery. Full registration and randomization will occur immediately following surgery, if nerve bundles have been spared.

Postoperative consent: Patients may also consent to the study up to 6 weeks postoperatively at which point they will be registered and randomized immediately following informed consent in clinic.

The blind 50 mg pills will be taken last thing at night, before the patient goes to bed without sexual stimulation (100 mg will be used for sexual relations). Thus, the chances of a man having an erection that would "unblind" him is remote. Furthermore, in the first 9 months after surgery, very few men will respond to any PDE5 inhibitor medication because of the intra-operative transient nerve injury. Finally, it takes on average, one hour before an erection can occur, and this must be in the setting of sexual stimulation. Thus, the patient will likely be asleep at this time. Hence, we believe that patients will remain blinded to whether they are on active or placebo sildenafil. Nonetheless, blinding will be assessed at the end of the study.

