14.3 Data Analysis

Summary statistics will be calculated, by group, for age, surgery (open or laparoscopic), tumor characteristics (stage, grade, PSA), baseline erectile function and quality of life scores. Compliance and off-study use of medications for erectile function will be described by group and follow-up time. Biochemical recurrences will be described separately by group using Kaplan-Meier methods.

The primary analysis will compare the erectile function domain score of the IIEF at 24 months. Secondary endpoints include:

- 1. EF scores at other time-points
- 2. The proportion of patients who have normalization of their erectile function, defined as a score of 26 or greater on the EF domain of the IIEF at any point during the study
- 3. Time for response to sildenafil (as defined by diary)
- 4. Time to return of spontaneous functional erections (as defined by diary)

(RB PB

IRB#: 09-005 A(10)

The primary comparison and secondary comparison 1 will be made by analysis of covariance with baseline score and randomization strata as the covariates. Secondary endpoint 2 will be compared by Fisher's exact test. Secondary endpoints 3 and 4 will be compared between groups by log rank. Three pairwise comparisons will be made: nightly sildenafil vs. PRN sildenafil; combination treatment vs. PRN sildenafil; nightly sildenafil vs. combination treatment.

As an additional analysis, we will model EF scores over time using Generalized Estimating Equations with time, treatment, time by treatment and baseline score as predictors. Treatment will be entered as two dummy variables: nightly sildenafil (coded 0 in the PRN group and 1 otherwise) and injection therapy (coded 1 in the combination group and 0 otherwise).

All analyses will be on the intention-to-treat principle with patients analyzed in their randomized groups regardless of the treatment actually received. All comparisons between combination and PRN sildenafail, and between nightly and PRN sildenafil, will use a 2.5% alpha; all comparisons between the two treatment arms will use a 90% non-inferiority bound.

The nature, severity and day of onset of adverse effects will be described along with assessment of causality.

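### Secondary endpoint 3 (time to respond to sildenafil) is ascertained unequally by design, so its two log-rank comparisons with the combination arm lean against combination

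*Combined protocol and SAP*

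**What the plan says.** Section 14.3 names secondary endpoint 3 as "Time for response to sildenafil (as defined by diary". Section 2.1 words the same objective as "The time for patients to respond to oral erectogenic therapy". On the test, 14.3 states "Secondary endpoints 3 and 4 will be compared between groups by log rank" and then "Three pairwise comparisons will be made: nightly sildenafil vs. PRN sildenafil; combination treatment vs. PRN sildenafil; nightly sildenafil vs. combination treatment". Section 14.2 also applies three analyses to every endpoint. Comparisons with PRN use a 2.5% alpha, and nightly v combination uses a 90% non-inferiority bound. All analyses are by intention to treat.

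The means available for sex differ by arm:

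- **PRN and nightly.** Section 4.2 says of the PRN arm: "They will be given six 100 mg doses, per month, for a 12 month duration". The nightly arm has the same supply.
- **Combination.** No as-needed sildenafil supply is listed. Section 1.1 says "Injection therapy can be used for the purposes of sexual relations". Sildenafil in this arm is 50 mg every night for the first two weeks (4.4), then 50 mg on the four nights a week without an injection.
- **After month 12.** Section 10.0 stops scheduled treatment and lets men in any arm use as-needed sildenafil or injections for sex, through their treating physician.

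Section 10.0 has the diary record, for each sexual encounter, the agent, dose, penetration and rigidity. Section 4.3 expects that "in the first 9 months after surgery, very few men will respond to any PDE5 inhibitor medication".

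**The concern.** A diary can show a response to sildenafil only when sildenafil was the agent used at a sexual encounter. The plan gives two arms a monthly supply for exactly that purpose and gives the third arm a different aid. A combination man whose erectile tissue has recovered as well as anyone's has fewer planned occasions on which that recovery could count as an event. If he stays on injections after month 12, he may never be observed for the event, yet under intention to treat he remains in the risk set as a non-responder. Section 14.3 makes no allowance for this.

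Two of the three comparisons would then partly measure which agent was dispensed for sex. The direction matters because section 14.2 says injections will not be recommended as required unless nightly sildenafil is shown to be inferior to combination. A test that makes combination look slow supports that conclusion whether or not it is true.

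**Working it through.** **No plan figure to reproduce.** The documents state no event rate, hazard ratio or power for endpoint 3. The power figures in 14.2 concern the IIEF-EF score at 24 months and do not bear on this point.

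**Opportunity to show the event, by arm**

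| | PRN (n = 40) | Nightly (n = 80) | Combination (n = 80) |
|---|---|---|---|
| 100 mg doses supplied for sex, months 0–12 | 6 × 12 = 72 | 6 × 12 = 72 | none listed |
| Other sildenafil, months 0–12 | none (placebo) | 50 mg at night | 50 mg nightly for 2 weeks, then 4 nights a week |
| Named aid for sex, months 0–12 | sildenafil 100 mg | sildenafil 100 mg | injection |
| After month 12 | sildenafil or injection | same | same |

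Section 4.2 expects about 4,000 mg per PRN man over the year, that is 4,000/100 = 40 as-needed doses.

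**Expected event counts with no true difference.** Assume 30% are responsive by month 12 and 50% by month 24 in every arm, and that no combination response is visible before month 12.

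- By month 12: nightly 0.30 × 80 = 24, PRN 0.30 × 40 = 12, combination 0.
- By month 24: nightly 0.50 × 80 = 40, PRN 0.50 × 40 = 20. Combination has 40 if all try sildenafil, 0.75 × 40 = 30 if 25% never do, and 0.60 × 40 = 24 if 40% never do.

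**Simulated log rank.** The statistic is Z = Σ(d₁ − d·n₁/n)/√V, with V = Σ d(n₁/n)(1 − n₁/n)(n − d)/(n − 1), summed over event times. True response times are identical in the arms. Hidden early responses in combination appear at month 12 plus 0–3 months, and men who never use sildenafil after month 12 show no later event. Censoring is at month 24, and the test is two-sided at 2.5%.

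*Set A.* Assumed response: 5–15% by month 9, 20–40% by month 12, 50–60% by month 24. There were 2,000–3,000 trials per scenario, run twice independently. The figures are total false rejection (nominal 2.5%), as the range over both runs.

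| Combination men never trying sildenafil | v nightly | v PRN |
|---|---|---|
| 0% | 3–12% | 3–12% |
| 25% | 32–65% | 25–51% |
| 50% | 88–99% | 75–92% |
| 25%, half of early responses visible on 50 mg nights (one run) | 19–22% | 13–21% |
| 50%, half visible (one run) | 61–66% | 48–50% |

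*Set B.* Assumed response: 5–10% by month 9, 15–40% by month 12, 45–60% by month 24. There were 800 trials per scenario. The figures are false findings that combination is slower (nominal 1.25%; Monte Carlo standard error there √(0.0125 × 0.9875/800) = 0.4 points).

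| Early combination responses visible | Never use after month 12 | v nightly | v PRN |
|---|---|---|---|
| none | 0% | 1.8–10.7% | 2.5–11.0% |
| none | 40% | 59.6–91.5% | 43.6–79.4% |
| half | 0% | 1.5–5.5% | 1.4–5.2% |
| half | 40% | 33.6–49.4% | 26.3–33.6% |
| all | 0% | 1.3–1.9% | 0.6–1.9% |
| all | 40% | 6.8–21.5% | 6.8–15.5% |

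Wherever combination responses are hidden or delayed, the lean is against combination. The first-year gap alone does little, because few responses are expected before month 9 and late events largely make up the deficit. Continued injection use after month 12 does most of the damage.

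The nightly v combination columns are illustrative. The plan uses a 90% non-inferiority bound there, and the margin in 14.2 is in IIEF-EF points, with none given for a time-to-event outcome.

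**The case against.** A reader might infer that the event cannot occur in the combination arm for 12 months. The documents do not support that. These men take 50 mg nightly for two weeks and then four nights a week. No section bars sex on those nights, section 9.0 encourages sexual relations, and the diary would record the agent and dose. Permission to use injections for sex does not make them the only means. The remark in 4.3 about taking the pill without sexual stimulation concerns the blinded pills, and the combination arm's 50 mg is not described as blinded. Section 14.3 also anticipates off-study use. What remains is that the plan supplies no sildenafil for sex in this arm, so the opportunity is smaller rather than absent.

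Three further objections have force:

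- The definition of response may sit in the diary (Appendix B), which is listed but not reproduced. A definition there would not by itself equalise the supply for sex.
- The larger error rates need a share of combination men who never try sildenafil after month 12, and the documents give none. All arms have the same access from then on.
- Treating the oral arms as fully observed is an idealisation, since 4.2 expects most PRN men to take no sildenafil in the first three months.

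These limit the size that can be claimed. They do not remove the unequal opportunity or change its direction.

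**Conclusion.** The point holds as one of unequal ascertainment. Following the plan as written gives two log-rank comparisons that lean against combination, and in nightly v combination the lean favours a non-inferiority conclusion for nightly.

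The size is uncertain. With no true difference, false rejection at a two-sided 2.5% level is about 3–12% if all combination men try sildenafil soon after month 12, and about 25–65% if a quarter never do. It is lower if responses on 50 mg nights count, and near nominal if every early response is visible and all men use sildenafil afterwards. Response rates, visibility on 50 mg nights and later uptake are all assumptions.

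A reader might take the highest simulated rates, near 90% and above, as the error rate of the planned test. They are not: they require 40–50% of combination men never to try sildenafil, and for nightly v combination they use a criterion that the plan does not. The primary endpoint is not affected.

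**What to change.** In 14.3, make nightly v PRN the only formal log-rank comparison for endpoint 3. These two arms have the same sildenafil supply for sex. Label combination v PRN and nightly v combination as descriptive for this endpoint. Suggested wording:

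*For secondary endpoint 3, the log-rank test will be applied formally to nightly v PRN sildenafil only. Results involving the combination arm are descriptive, because that arm is not supplied sildenafil for sexual relations during the first 12 months. The number of men in each arm recording at least one sildenafil-aided attempt will be tabulated for months 0–12 and 12–24.*

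That count is context only. Men who attempted sildenafil are selected after randomisation and should not become the denominator of a between-arm comparison.

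Formal combination comparisons could be kept only if the event is defined in the analysis section (criterion, dose and setting that count) so that all arms have the same chance to show it. State the limit beside the endpoint in 2.1.

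The cost is a wording change in two sections. No new data are needed, since the diary already records the agent at each encounter. The downside is that two secondary comparisons lose formal inferential status.

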14.1 BIOSTATISTICS

14.2 Sample Size

For each endpoint we will conduct three analysis:

- 1. A comparison of nightly sildenafil to PRN sildenafil with an alpha of 2.5%
- 2. A comparison of combination treatment to PRN sildenafil with an alpha of 2.5%
- 3. A non-inferiority comparison between nightly sildenafil and combination treatment: in this analysis, nightly sildenafil will be considered non-inferior to combination treatment if the upper bound of a 90% confidence interval for the difference between groups does not include combination treatment being at least three points superior to nightly sildenafil.

(RB PB

Amended: 02/12/13

- 15 -

IRB#: 09-005 A(10)

Our rationale is for the different comparisons is as follows. We want to know whether the two active arms (nightly sildenafil and combination treatment) are superior to control (PRN sildenafil). We will therefore test each against control using an alpha half of the conventional value to account for multiple testing. Furthermore, combination treatment, which involves penile injection, is less tolerable for patients than nightly sildenafil, which only involves oral medication. Therefore unless nightly sildenafil is demonstrably inferior to combination treatment, we will recommend that injections are not required. Hence we will conduct a non-inferiority comparison between the two active arms.

Our primary endpoint is the IIEF-EF at 24 months. Based on previous studies, we estimate that the SD for the IIEF-EF will be 9 points. Prior data at MSKCC suggest that the correlation between baseline and follow-up IIEF-EF will be small enough as to have a negligible effect on variance. The minimum, clinically significant difference between active and control arms is 6 points based on our clinical experience and discussion held with [name] the designer of the IIEF. If we obtain data from 80 patients on each of the two active arms (nightly sildenafil and combination therapy) and 40 patients on the control arm (PRN sildenafil), we will have 89% power for the comparison between active and control and 80% power for the non-inferiority comparison between active arms.

MSKCC surgeons do approximately 850 radical prostatectomies per year. We estimate that 50% of patients will be eligible for the study. Assuming that 25% - 33% of eligible patients enroll, we should complete accrual within 18-24 months.

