15.3 Randomization

This is a randomized comparison of PRN sildenafil arm (Group 1), nightly sildenafil arm (Group 2), and Combination arm (Group 3). After eligibility has been established and immediately after consent has been obtained, patients will be registered to the study in the Protocol Participant Registration (PPR) system and randomized using the Clinical Research Database (CRDB). Randomization will be accomplished by the method of random permuted blocks with varying block size, stratified by surgeon. A total of 3 surgeons at MSKCC will perform the nerve sparing RP for a total of 3 strata.

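### Secondary endpoints 2 to 4 are tested without the surgeon strata used in randomization and in the ANCOVA; if surgeon is prognostic, these tests lose power that stratified versions would recover

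*Combined protocol and SAP*

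**What the plan says.** Section 15.3 (Randomization) of the combined protocol and SAP: "Randomization will be accomplished by the method of random permuted blocks with varying block size, stratified by surgeon". It adds: "A total of 3 surgeons at MSKCC will perform the nerve sparing RP for a total of 3 strata".

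Section 14.3 (Data Analysis) carries those strata into the EF-score analyses: "The primary comparison and secondary comparison 1 will be made by analysis of covariance with baseline score and randomization strata as the covariates". Secondary comparison 1 is the EF score at the other time-points.

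The next sentences of 14.3 cover the other three secondary endpoints. For endpoint 2, normalization, "defined as a score of 26 or greater on the EF domain of the IIEF at any point during the study", the plan names Fisher's "exact test. Secondary endpoints 3 and 4 will be compared between groups by log rank". Endpoints 3 and 4 are time to response to sildenafil and time to return of spontaneous functional erections. Neither sentence names a stratum or a covariate.

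Each active arm (80 men) is compared with PRN sildenafil (40 men) at an alpha of 2.5%. Section 14.2 states power for the primary endpoint only. It also says of baseline EF that "the correlation between baseline and follow-up IIEF-EF will be small enough as to have a negligible effect on variance".

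**The concern.** The plan treats surgeon as important enough to stratify on and to put in the ANCOVA, then leaves it out for three of the four secondary endpoints without giving a reason. Stratified randomization balances the arms within surgeon. A test that ignores surgeon still counts surgeon-to-surgeon variation as noise in the treatment comparison, so its variance is too large and it rejects too rarely.

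At stake is the chance of detecting a real benefit in normalization or in recovery time. The comparisons already rest on 40 PRN men and a halved alpha.

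**Working it through.** **Inputs from the documents.** 80 v 40 men; alpha 2.5% per active-v-PRN comparison; SD 9; difference 6 points; 3 surgeon strata; 24 months of follow-up.

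**Inputs assumed.** Event rates, treatment effects on endpoints 2 to 4, surgeon effects and equal surgeon volumes. The documents give none of these. Dropout is not modelled.

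**1. The plan's own figure.** SE = 9 × √(1/40 + 1/80) = 1.743, and 6/1.743 = 3.443. Two-sided 2.5% has critical value 2.241, so power = Φ(3.443 − 2.241) = Φ(1.20) = 88.5%. This matches the stated 89%. One-sided 2.5% would give 93.1%. Two-sided 2.5% is therefore used below.

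**2. Fisher's test with no surgeon effect.** Exact enumeration of all 80 v 40 tables gives the true size at a nominal 2.5%:

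| Common rate | Fisher | Pearson chi-square |
|---|---|---|
| 10% | 1.47% | 2.07% |
| 20% | 1.71% | 2.42% |
| 30% | 1.95% | 2.41% |
| 40% | 1.89% | 2.49% |
| 50% | 1.92% | 2.37% |

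This is discreteness and has nothing to do with strata.

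**3. Endpoint 2 with surgeon effects.** Assumed 30% v 55%, 20,000 runs, simulation SE about 0.3 points on power and 0.1 on size:

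| Surgeon log-odds | Fisher power | Pearson power | Mantel-Haenszel by surgeon, power | Fisher size | Mantel-Haenszel size |
|---|---|---|---|---|---|
| none | 62.7% | 64.6% | 64.8% | 2.0% | 2.6% |
| ±0.5 (OR 2.7 between extremes) | 60.1% | 62.4% | 65.8% | 1.7% | 2.3% |
| ±1.0 (OR 7.4) | 59.1% | 61.1% | 71.0% | 1.4% | 2.6% |

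The Pearson column separates the two causes. Fisher to Pearson is discreteness: 1.9, 2.3 and 2.0 points. Pearson to Mantel-Haenszel is the omitted strata: 0.2, 3.4 and 9.9 points.

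A second setting (log-odds ratio 1.1, PRN rate near 30%) gives Fisher 66.7% v Mantel-Haenszel 69.1% with no surgeon effect, and 60.1% v 67.1% at ±0.6. Of that last gap of 7.0 points, 2.4 are present with no surgeon effect, which leaves about 4.6 for the strata.

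**4. Endpoints 3 and 4.** Assumed treatment HR 2, about 85 to 88 events, 2,500 runs, simulation SE about 0.9 points on power and 0.3 on size:

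| Surgeon log-hazard | Unstratified power | Stratified power | Unstratified size | Stratified size |
|---|---|---|---|---|
| none | 76.8% | 76.0% | 3.3% | 3.1% |
| ±0.25 (HR 1.65 between extremes) | 70.2% | 72.5% | 2.6% | 2.3% |
| ±0.5 (HR 2.7) | 66.1% | 74.6% | 2.4% | 2.7% |
| ±0.75 (HR 4.5) | 52.1% | 71.9% | 1.2% | 2.4% |

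Stratifying changes power by −0.8, +2.3, +8.5 and +19.8 points. The no-effect sizes of 3.3% and 3.1% are simulation noise: a longer repeat of the same model puts both tests at nominal.

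With treatment HR 1.8 instead, ±0.5 gives 44.5% unstratified v 54.2% stratified (+9.7), and no surgeon effect gives 53.4% v 52.8% (−0.6).

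**5. Baseline EF.** In the second setting of step 3, add a baseline effect in which 35% of men enter at 22–25 with log-odds 1.0 lower. Stratifying by surgeon alone then gives 62.2%, and by surgeon and baseline 63.6%, a gain of 1.4 points. A separate simulation (log-odds ratio 1.1, PRN intercept −0.5) with no surgeon or baseline effect shows a loss, 70.8% to 70.0%. On the primary analysis, residual SD = 9√(1 − ρ²) gives power 88.9% at ρ = 0.1 and 89.8% at ρ = 0.2, against 88.5% with none.

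**The case against.** The strongest reply is that nothing here is invalid. Fisher's test and an unstratified log rank do not inflate type I error after stratified randomization, the endpoints are secondary, and a simple prespecified test is a defensible choice. That stands, and it sets the severity. Being safe against false positives does not make the tests efficient, however, and the stratified versions need no new data.

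Three further objections limit the point:

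- **The loss depends on an unknown surgeon effect.** A reader might infer that these tests are conservative and weak whatever the data. The documents do not support that for the log rank, which is no weaker when surgeon does not matter. At log-hazards of ±0.5 its simulated size of 2.4% cannot be told apart from 2.5%. A shortfall in size is clear in these runs only at ±0.75.
- **Part of Fisher's deficit is not about strata.** With a small surgeon effect (log-odds ±0.25, plus a baseline effect of 0.3), Fisher has 64.4%, an unstratified score test 68.6% and Mantel-Haenszel by surgeon 70.1%. So 4.2 of the 5.7 points come from leaving an exact test and 1.5 from the strata. Preferring an exact test is legitimate.
- **Baseline EF is not shown to matter.** It is tempting to argue that men entering at 22–25 must exceed their own baseline to reach 26, so baseline must be adjusted for as well. Section 14.2 expects a negligible baseline correlation. That statement concerns the variance of the continuous score, so it does not rule out a threshold effect, but the documents offer no evidence of one. The gain is about 1 point even under a favourable assumption. Men who consent after surgery also complete the baseline questionnaire retrospectively (section 8.0).

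Finally, section 14.3 says log rank without calling it unstratified. Since the preceding sentence names the strata where they are wanted, unstratified is the natural reading. If a stratified test was meant, the sentence should say so.

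**Conclusion.** The point holds in a conditional form and is minor. Section 14.3 leaves the surgeon strata out of the tests for endpoints 2 to 4. If surgeon is prognostic, this costs about 2 to 3 points of power at modest effects. At log-hazards of ±0.5 or log-odds of ±0.6 the gap to the stratified tests is 7 to 10 points, and the endpoint 2 part of that includes roughly 2 points of Fisher's discreteness. If surgeon has no effect, the log rank loses nothing. Fisher's true size of 1.5% to 2.0% at 80 v 40 is a separate matter and holds with or without strata.

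The power figures rest on assumed rates, treatment effects and surgeon effects, equal surgeon volumes and no dropout. The Fisher size rests only on 80 v 40 and a two-sided 2.5%, over common rates of 10% to 50%. The primary endpoint and the EF scores at other time-points are unaffected.

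**What to change.** In 14.3, for the comparisons of each active arm with PRN sildenafil at the existing 2.5%:

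- Compare endpoint 2 by a Mantel-Haenszel test stratified by surgeon, or by logistic regression with surgeon as a factor. Baseline EF may be added, with little expected gain.
- Compare endpoints 3 and 4 by a log-rank test stratified by surgeon.
- Keep Fisher's test and the unstratified log rank as sensitivity analyses.

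The cost is a wording change made before unblinding. No new data or patients are needed, because surgeon is already recorded for randomization. The downside is a loss of about 1 point of power or less for the log rank if surgeon has no effect, and an asymptotic test in place of an exact one for endpoint 2. With equal surgeon volumes each stratum would hold about 40/3 ≈ 13 PRN men, which is workable for three strata.

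This change does not supply the 90% non-inferiority bound that 14.3 asks for between nightly sildenafil and combination treatment. On these endpoints that bound needs its own effect measure and margin.
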